9.3 DEMOGRAPHIC AND BASELINE CHARACTERISTICS

Baseline characteristics will include following parameters: age, sex, race, ECOG performance status, ISS stage (plasma albumin and serum-beta-2-microglobuline), paraprotein isotype, S- and U- paraprotein, S-FLC and ratio, hemoglobin, WBC, differential, platelet count, CRP, creatinine, calcium ionized, liver enzymes, LD, bone marrow morphology, bone marrow multiparameter flow cytometry, bone marrow cytogenetic analyses, FISH analyses t(4;14), +1q, cytogenetic del17p/p53 (if not previously diagnosed). Bone imaging will include skeletal ray or whole body low-dose CT, (MRI of spina and hip if clinically indicated).

10. STUDY MANAGEMENT

10.1 Compliance with the protocol

Principal investigators of each study site are responsible to follow the protocol and inform the principal investigator of whole study immediately of any possible protocol violations, any severe adverse events and any suspected unexpected

Helsinki University Hospital Comprehensive Cancer Center Hematology
Clinical study protocol NMSG#24/15

serious adverse reactions (SUSAR's). This is mandatory because so far there are not any information or experience regarding this elotuzumab plus carfilzomib and dexamethasone treatment in MM patients. Principal investigator must confirm that any protocol revisions or amendments will be noticed and followed in each study site.

10.2 PUBLICATION

The final results of this study will be written for the publication by principal investigator and the members of the study (principal investigators and coinvestigators of sites). This study will be registered with clinicaltrials.com. and negative and inconclusive as well as positive results will be written for publication. The companies BMS and AMGEN will have possibility to review the publication three weeks before submission but the publication is owned and written by academic investigators.

10.3 DESTRUCTION OF INVESTIGATIONAL PRODUCTS

Each study site will destruct the study drugs by detailed guidelines of destruction and all procedures will be documented by pharmacy of study site.

Helsinki University Hospital Comprehensive Cancer Center Hematology
 Clinical study protocol NMSG#24/15

APPENDIX 1. Eastern Cooperative Oncology Group (ECOG) Scale for Performance Status

Grade	Description
0	Normal activity. Fully active, able to carry on all predisease performance without restriction
1	Symptoms but ambulatory. Restricted in physically strenuous activity, but ambulatory and able to carry out work of a light or sedentary nature (eg, light housework, office work)
2	In bed < 50% of the time. Ambulatory and capable of all self-care, but unable to carry out any work activities. Up and about more than 50% of waking hours.
3	In bed > 50% of the time. Capable of only limited self-care, confined to bed or chair more than 50% of waking hours.
4	100% bedridden. Completely disabled. Cannot carry on any self-care. Totally confined to bed or chair
5	Dead

Source: Oken MM, Creech RH, Tormey DC, Horton J, Davis TE, McFadden ET et al. Toxicity and response criteria of the Eastern Cooperative Oncology Group. Am J Clin Oncol 1982; 5 (6):649-55.

APPENDIX 2.

Cockcroft-Gault Equation

For males:

$$\text{Creatinine Clearance} = \frac{(140 - \text{age}[\text{years}] \times \text{weight} [\text{kg}])}{72 \times (\text{serum creatinine}[\text{mg/dL}])} \text{ OR } \frac{(140 - \text{age}[\text{years}] \times \text{weight} [\text{kg}])}{0.81 \times (\text{serum creatinine}[\mu\text{mol/L}])}$$

For females:

$$\text{Creatinine Clearance} = \frac{0.85 (140 - \text{age}[\text{years}] \times \text{weight} [\text{kg}])}{72 \times (\text{serum creatinine}[\text{mg/dL}])} \text{ OR } \frac{0.85 (140 - \text{age}[\text{years}] \times \text{weight} [\text{kg}])}{0.81 \times (\text{serum creatinine}[\mu\text{mol/L}])}$$

Source: Cockcroft DW, Gault MH. Prediction of creatinine clearance from serum creatinine. Nephron 1976;16(1):31-41.

Helsinki University Hospital Comprehensive Cancer Center Hematology
Clinical study protocol NMSG#24/15

APPENDIX 3.

NEW YORK HEART ASSOCIATION CLASSIFICATION OF CARDIAC DISEASE (NYHA)

Class	Functional Capacity	Objective Assessment
I	Patients with cardiac disease but without resulting limitations of physical activity. Ordinary physical activity does not cause undue fatigue, palpitation, dyspnea, or anginal pain.	No objective evidence of cardiovascular disease.
II	Patients with cardiac disease resulting in slight limitation of physical activity. They are comfortable at rest. Ordinary physical activity results in fatigue, palpitation, dyspnea, or anginal pain.	Objective evidence of minimal cardiovascular disease.
III	Patients with cardiac disease resulting in marked limitation of physical activity. They are comfortable at rest. Less than ordinary activity causes fatigue, palpitation, dyspnea, or anginal pain.	Objective evidence of moderately severe cardiovascular disease.
IV	Patients with cardiac disease resulting in inability to carry on any physical activity without discomfort. Symptoms of heart failure or the anginal syndrome may be present even at rest. If any physical activity is undertaken, discomfort is increased.	Objective evidence of severe cardiovascular disease.

Source: The Criteria Committee of the New York Heart Association, Inc.: Diseases of the heart and blood vessels; Nomenclature and criteria for diagnosis, 6th Ed. Boston: Little, Brown; 1964.

APPENDIX 4. New international staging system (ISS) (Greipp et al. JCO 2005; 23: 3412-3420)

Stage	Criteria	Median survival months
I	Serum β_2 -microglobulin < 3.5 mg/l Serum albumin \geq 35 g/l	62
II	Not stage I or III*	44
III	Serum β_2 -microglobulin \geq 5.5 mg/l	29

* There are two categories for stage II: serum β_2 -microglobulin < 3.5 mg/l but serum albumin < 35 g/l; or serum β_2 -microglobulin 3.5 to 5.5 mg/l irrespective of the serum albumin level.

APPENDIX 5. This study is for relapsed/progressed MM patients, but CRAB criteria are included as a basic information: Rajkumar SV et al. Lancet Oncol 2014;15:e538-48

Multiple myeloma	
Clonal bone marrow plasma cells $\geq 10\%$ or biopsy-proven bone or extramedullary plasmacytoma and any one or more of the following myeloma defining events	

 • Myeloma defining events Evidence of end organ damage that can be attributed to the underlying plasma cell proliferative disorder, specifically: 
 1. Hypercalcemia: serum calcium > 0.25 mmol/l higher than the upper limit of normal or > 2.75 mmol/l 2. Renal insufficiency: creatinine clearance < 40 ml/min or serum creatinine > 177 μmol/l 3. Anemia: hemoglobin value of > 20 g/l below the lower limit of normal, or a hemoglobin value < 100 g/l 4. Bone lesions: one or more osteolytic lesions on skeletal radiography, CT or PET-CT 	

International Myeloma Working Group uniform response criteria by response subcategory for multiple myeloma (Rajkumar et al. Blood 2011;117(18):4691-4695)

Response	Response criteria ^a
sCR	CR as defined below plus Normal FLC ratio (0.26-1.65) and Absence of clonal cells in bone marrow ^b by immunohistochemistry or immunophenotyping ^c
CR	Negative IFE of serum and urine and Disappearance of any soft tissue plasmacytomas and $< 5\%$ plasma cells in bone marrow ^b In patients in whom the only measurable disease is by sFLC levels, CR is defined as a normal FLC ratio (0.26-1.65) in addition to the CR criteria listed above
VGPR	Serum and urine M-protein detectable by IFE but not on electrophoresis or 90% or greater reduction in serum M-protein plus urine M-protein level < 100 mg per 24h In patients in whom the only measurable disease is by sFLC levels, VGPR is defined as a $> 90\%$ decrease in the difference between involved and uninvolved sFLC levels
PR	$\geq 50\%$ reduction of serum M-protein and reduction in 24-h urinary M-protein by $\geq 90\%$ or to < 200 mg per 24 h In patients in whom the only measurable disease is by sFLC levels, PR is defined as a $\geq 50\%$ decrease in the difference between involved and uninvolved sFLC levels

Helsinki University Hospital Comprehensive Cancer Center Hematology
Clinical study protocol NMSG#24/15

	
If serum and urine M-protein are unmeasurable, and sFLCs are also unmeasurable, $\geq 50\%$ reduction in bone marrow plasma cells is required in place of M-protein, provided baseline percentage was $\geq 30\%$
 
In addition to the above listed criteria, if present at baseline, a $\geq 50\%$ reduction in the size of soft tissue plasmacytomas is also required

SD ^d	Not meeting criteria for CR, VGPR, PR or progressive disease

Abbreviations: CR, complete response; FLC, free light chain; IFE, Immunofixation; PR, partial response; SD, stable disease; sCR, stringent complete response; VGPR, very good partial response.

^a All response categories require two consecutive assessments made at anytime before the institution of any new therapy;

all categories also require no known evidence of progressive or new bone lesions if radiographic studies were performed.

^b Confirmation with repeat bone marrow examination not needed.

^c Presence/absence of clonal cells is based upon the κ/λ ratio. An abnormal κ/λ ratio by immunohistochemistry and/or immunofluorescence requires a minimum of 100 plasma cells for analysis. An abnormal ratio reflecting presence of an abnormal clone is κ/λ of $> 4:1$ or $< 1:2$.

^d not recommended for use as an indicator of response; stability of disease is best described by providing the time to progression estimates

NOTE: Once (s)CR is established, response remains (s)CR until relapse is documented.

RELAPSE CRITERIA

Relapse subcategory	Relapse criteria

Progressive criteria^a
 
To be used for calculation of time to progression and progression-free survival end points for all patients including those in CR (includes primary progressive disease and disease progression on or off therapy)
	
Progressive disease: requires one or more of the following: Increase of $\geq 25\%$ from lowest response value in serum M-component (the absolute increase must be $\geq 0.5\text{g/dl}$)^b and/or
 
Increase of $\geq 25\%$ from lowest response value in urine M-component (the absolute increase must be $\geq 200\text{mg/24 h}$) and/or
 
In patients in whom the only measurable disease is by sFLC levels, increase of $\geq 25\%$ from lowest response value in the difference between involved and uninvolved sFLC levels (absolute increase must be $> 100 \text{ mg/L}$)
 
If serum and urine M-protein are unmeasurable, and sFLC are also unmeasurable, increase of $\geq 25\%$ from lowest response value in bone marrow plasma cell percentage (absolute % must be $\geq 10\%$)
 
Definite development of new bone lesions or soft tissue plasmacytomas or definitive increase in the size of existing bone lesions or soft tissue plasmacytomas

Helsinki University Hospital Comprehensive Cancer Center Hematology
Clinical study protocol NMSG#24/15

	Development of hypercalcemia (corrected serum calcium > 11.5 mg/dl or 2.65 mmol/l) that can be attributed solely to the plasma cell proliferative disorder
Clinical relapse ^a	
Clinical relapse requires one or more of:
 
Direct indicators of increasing disease and/or end organ dysfunction (CRAB features)^b. It is not used in calculation of time to progression or progression-free survival but is listed here as something that can be reported optionally or for use in clinical practice
 
 1. Development of new soft tissue plasmacytomas or bone lesion 2. Definite increase in the size of existing plasma- cytomas or bone lesions. A definite increase is defined as a 50% (and at least 1 cm) increase as measured serially by the sum of the products of the cross-diameters of the measurable lesion. 3. Hypercalcaemia (> 2.65 mmol/l) (11.5 mg/dl) 4. Decrease in hemoglobin of ≥ 1.25 mmol/l (2 g/dl) 5. Rise in serum creatinine by 177 μmol/l or more (2 mg/dl or more) 6. Hyperviscosity
Relapse from CR ^a (To be used only if the end point studied is DFS) ^d	
Any one or more of the following
 
Reappearance of serum or urine M-protein by immunofixation or electrophoresis
 
In patients in whom the only measurable disease is by sFLC levels, reappearance of abnormal sFLC levels (absolute increase must be > 100 mg/L)
 
Development of $\geq 5\%$ plasma cells in the bone marrow^c
 
Appearance of any other sign of progression (i.e., new plasmacytoma, lytic bone lesion, or hypercalcemia see above)

Abbreviations: CR, complete response; DFS, disease-free survival.

^a All relapse categories require two consecutive assessments made at anytime before classification as relapse or disease progression and/or the institution of any new therapy.

^b For progressive disease, serum M-component increases of ≥ 10 g/l are sufficient to define relapse if M-component is ≥ 50 g/l.

^c Relapse from CR has the 5% cutoff versus 10% for other categories of relapse.

^d For purposes of calculating time to progression and progression-free survival, CR patients should also be evaluated using criteria listed above for progressive disease

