6.4 Blood chemistry

- creatinine, creatinine clearance (Cockcroft-Gault equation)
- liver enzymes (ALAT, AFOS, BIL)
- plasma albumin (ISS)
- serum beta-2-microglobulin (ISS, Appendix 4)
- LD
- CRP
- Ionized calcium, sodium, potassium, phosphate
- Uric acid
- E-Coombs (direct antiglobulin test, DAT) at screening and repeated if clinically unexpected anemia appears

Blood, bone marrow, and urine samples will be required at study entry and at key time-points during the treatment for biochemical, and immunophenotypic assessments, as part of scientific studies in order to monitor MRD as defined by paraprotein, serum free light chain and flow cytometry to define depth and quality of responses. In addition, cytogenetic FISH findings are utilized as prognostic and stratification markers.

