9.1 ENDPOINT DEFINITIONS

Primary endpoint of this study is overall response rate

Secondary endpoints are

- Complete remission (CR) rate
- Quality of response (proportion of MRD negativity in patients with at least VGPR)
- Duration of responses including MRD negativity
- Progression-free survival (PFS)
- Time to next treatment (TTNT)
- Safety (Adverse events)

Minimal residual disease (MRD) will be assessed by 8-colour EuroFlow multiparameter flow cytometry if at least VGPR has been achieved.

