9.2 STATISTICAL AND EFFICACY ANALYSES

Statistical analyses will be performed on intention-to-treat and on per-protocol-treated principle. Patients who have been included in the study but been withdrawn before any study drug administration are not included in analyses. Safety and efficacy analyses will be done for all patients who have received at least a single dose of study drug. Any spurious data will be abandoned. Missing

Helsinki University Hospital Comprehensive Cancer Center Hematology
Clinical study protocol NMSG#24/15

data will be handling as missing data not with replacing it with a median parameter number.

Efficacy analyses will be done using International Myeloma Working Group response criteria (Appendix 5). Response will be assessed before each cycle. Progression will be assessed using IMWG criteria for progressive disease.

For classification the adverse events NCI CTCAE version 4.0 will be used. Threshold for safety of this CAR-ELO-Dex combination is considered to be less than 70% of grade ≥ 3 non-hematological adverse events.

Efficacy, safety and QoL analysis will be performed when last patient in has been treated for two years in the study. Kaplan-Meier method will be used to estimate the time to event analyses. The PFS, TTNT and duration of response will be calculated from the start of the first dose of study drug combination.

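### Appendix 5 gives the hypercalcaemia limit for progressive disease as two different calcium levels, and the listed laboratory tests provide ionized rather than corrected serum calcium

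*Protocol*

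**What the plan says.** Section 9.2 of the Protocol states: "Progression will be assessed using IMWG criteria for progressive disease". Those criteria are reproduced in the relapse table of Appendix 5, where the progressive-disease row carries the instruction "To be used for calculation of time to progression and progression-free survival end points for all patients". Any one listed item is enough. One item is "Development of hypercalcemia (corrected serum calcium > 11.5 mg/dl or 2.65 mmol/l", with the condition that the hypercalcaemia be attributable only to the plasma cell disorder. A footnote to the table asks for two consecutive assessments in every relapse category.

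The clinical-relapse row of the same table has "Hypercalcaemia (> 2.65 mmol/l) (11.5 mg/dl". That row says of itself that it is not used for time to progression or PFS and may be reported optionally.

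PFS is among the secondary endpoints in Section 9.1. Section 4 continues treatment cycles until progression, relapse or excess toxicity.

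On measurement, the blood chemistry list in Section 6.4 has "Ionized calcium, sodium, potassium, phosphate", and the baseline list in Section 9.3 has "creatinine, calcium ionized, liver enzymes, LD". Albumin is in the 6.4 list, annotated for ISS staging. Table 1 schedules blood chemistry at screening, on day 1 of each cycle and at end of study, without itemising it. The shorter safety panel used between those visits contains no calcium.

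**The concern.** A limit printed in two units should be one limit. If the two figures are different levels, whether a patient has progressed depends on which figure the assessor reads. The criterion can establish progression by itself, so the choice could decide whether and when a PFS event is recorded and whether treatment stops.

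A second question comes before the first: does the trial collect the quantity that the criterion is written for? Corrected serum calcium is total calcium adjusted for albumin. Ionized calcium is a different quantity with its own scale, and the Protocol gives neither a limit for it nor a conversion.

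**Working it through.** **Inputs**

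- Progressive-disease limit, Appendix 5: 11.5 mg/dl or 2.65 mmol/l.
- The same pair under clinical relapse, with the mg/dl figure in brackets after the mmol/l figure, so it is meant as one level in two units.
- Molar mass of calcium, 40.078 g/mol (a physical constant, not from the Protocol).

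**Formula**

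mmol/l = mg/dl × 10 / 40.078 = mg/dl × 0.2495.

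**Attempt to reproduce the printed pair**

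- 11.5 × 0.2495 = 2.87 mmol/l, against 2.65 printed.
- 2.65 / 0.2495 = 10.62 mg/dl, against 11.5 printed.
- Gap: 2.869 − 2.65 = 0.219 mmol/l; 11.5 − 10.62 = 0.88 mg/dl; 0.219 / 2.65 = 8.3%.

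The pair does not reproduce.

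**Can rounding or the conversion factor explain it?**

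- With the round factor 0.25: 11.5 × 0.25 = 2.875 mmol/l and 2.65 / 0.25 = 10.60 mg/dl.
- If 11.5 stands for anything from 11.45 to 11.55 mg/dl, the range is 2.86 to 2.88 mmol/l.
- If 2.65 stands for anything from 2.645 to 2.655 mmol/l, the range is 10.60 to 10.64 mg/dl.

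The ranges do not come near each other, so neither explains the gap.

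**Do the neighbouring unit pairs convert?**

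- Creatinine: 2 mg/dl × 88.4 = 176.8 µmol/l; printed 177.
- Haemoglobin: 2 g/dl = 20 g/l, and 20 / 16.114 = 1.24 mmol/l; printed 1.25.

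Both agree to rounding. In this list only the calcium pair fails.

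**What the gap does to a classification**

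Take a corrected calcium of 2.70 mmol/l, confirmed and attributed solely to myeloma. In the other unit it is 2.70 / 0.2495 = 10.82 mg/dl. It exceeds 2.65 mmol/l and falls short of 11.5 mg/dl. The same holds for any value above 2.65 and up to 2.87 mmol/l.

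**Criterion against assay**

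| Item | Calcium measure |
|---|---|
| Progressive-disease criterion, Appendix 5 | corrected serum calcium |
| Blood chemistry, Section 6.4 | ionized calcium |
| Baseline characteristics, Section 9.3 | ionized calcium |
| Interim safety panel, Table 1 | none |

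Total serum calcium is listed nowhere. Of the two quantities needed for a corrected value, total calcium and albumin, only albumin is listed.

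**The case against.** The strongest reply concerns consequence. The hypercalcaemia must be due solely to the plasma cell disorder and must be seen twice. Every patient enters with measurable serum M-protein, urine M-protein or free light chains (inclusion criterion 2), and Sections 6.5 and 9.2 have the M-component and free light chains measured whenever response is assessed, which is before each cycle. The calcium limit moves a PFS date only if confirmed, myeloma-attributed hypercalcaemia in the narrow band comes before every other criterion. All of this stands, and it keeps the point modest.

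It can also be said that all sites are in Finland and Sweden. If they all report in mmol/l, which the Protocol does not state, patients are classified alike. That is fair: a reader might infer that the criterion cannot be applied consistently, but the text does not establish that. Under uniform use of one unit, what remains is that the printed pair is internally wrong. Reading the word between the figures as a true alternative does not rescue it either: the lower figure would then always decide and the higher one would do nothing, and the bracketed form under clinical relapse shows that equivalents were meant.

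On the assay, nothing stops a site from measuring total calcium locally when hypercalcaemia is suspected. That stands as well, but the Protocol does not ask for it.

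Three further inferences are tempting and not supported. First, Appendix 5 also prints "serum calcium > 0.25 mmol/l higher than the upper limit of normal or > 2.75 mmol/l"; this belongs to the criteria for myeloma-defining events, is included as background, and need not equal a progression limit, so it is no contradiction. Second, the repeated pair under clinical relapse might be taken as a second route into PFS; that row excludes itself from PFS. Third, inclusion criterion 4 refers to Appendix 5, but it accepts paraprotein or CRAB evidence, and nothing shows a patient whose eligibility turns on this band.

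**Conclusion.** The point holds in a limited form. As written, the hypercalcaemia criterion for progressive disease contains two limits 0.22 mmol/l (0.88 mg/dl, about 8%) apart, and values above 2.65 and up to 2.87 mmol/l are progression by one and not by the other. The arithmetic rests only on the molar mass of calcium and does not depend on rounding. Independently, the listed laboratory tests name ionized calcium, to which neither limit applies directly.

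The effect on PFS is probably small and cannot be quantified, because the Protocol gives no frequency for progression on calcium alone. One affected patient would be 1 of 40 (2.5%), which sets the scale but is not an estimate. The primary endpoint, ORR, is touched at most marginally. The pair may have been carried over from the cited consensus criteria; that source is not at hand, and the inconsistency stands in the text that sites must apply whatever its origin. The documents do not settle which limit was intended, and no view is taken here.

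**What to change.** 1. In Appendix 5, reconcile the two calcium figures in both the progressive-disease row and the clinical-relapse row, so that one limit is stated and the figure in the other unit is its correct conversion. Which limit to keep is for the investigators to decide against the criteria that they mean to follow.
2. Align the calcium measure in Sections 6.4 and 9.3 with the criterion: either list total serum calcium, to be corrected with the albumin already in the 6.4 list, or state which calcium measure the criterion uses.

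The cost is a text correction in two places and at most one added assay. The albumin entry is annotated for staging, so if correction is chosen, 6.4 should make clear that albumin is measured whenever calcium is. Because the limit defines a PFS event, the change should go through the amendment process in Section 8.2, with ethics committee and regulatory approval, and can be combined with any other amendment.
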